4.8 Interruption or Discontinuation of Study Dosing and Randomization

If any of the following events occurs, no further administration of study drug will take place and no further patients will be entered or randomized into that cohort or any higher dose cohort until the event has been reviewed by the Medical Monitor and the SMC.

- Death of any patient in which the cause is determined by the investigator or the sponsor to be related to study drug; or death of any patient which, in the opinion of the sponsor, contraindicates further dosing;
- Any life-threatening clinical event related to the study drug, including anaphylactic reaction to study drug, Grade 4;
- Serious clinical infections with a virus of the herpes family (including disseminated herpes infection, herpes encephalitis, or ophthalmic herpes infection) or with CMV or EBV in any patient; or
- Any event that, in the opinion of the Medical Monitor, contraindicates further dosing of study subjects.

If one of the above-listed events occurs, a prompt cumulative review of safety data and the circumstances of the event in question will be conducted by the Medical Monitor and the SMC to determine whether dosing and study entry should be resumed, the protocol modified, or

discontinued permanently. SMC review and approval are required for resumption of the study if study dosing and entry are stopped due to one of the above-listed events.

4.9 Dose Escalation

The rules for dose escalation are as follows:

Dose Cohort 1 (single-dose, 0.3 mg/kg or placebo) will be started first. Dosing at each next higher dose cohort (Dose Cohort 2 [1.0 mg/kg or placebo], Dose Cohorts 3A and 3B [3.0 mg/kg or placebo], and Dose Cohort 4 [10.0 mg/kg or placebo] will commence after the Medical Monitor has reviewed the safety information including data through Study Day 42 from the first randomized 8 patients in each of the preceding lower dose cohorts and all cumulative safety data available in all cohorts, and has determined that the safety profile is acceptable (ie, Dose Cohort 2 will start only after safety data from the 8 patients in Dose Cohort 1 has been reviewed and it has been deemed safe; likewise, Dose Cohorts 3A and 3B will start only after the data from the 8 patients in Dose Cohort 2 has been reviewed and it has been deemed safe; Dose Cohort 4 will start only after safety data from the 8 patients from Dose Cohort 3A have been reviewed and it has been deemed safe). Dose Cohorts 3B and 4 will enter patients in parallel.

Available PK data from study MI-CP126 indicated that MEDI-545 has a serum half-life of 15 to 18 days and a linear increase in serum concentrations with dose. As such, the serum MEDI-545 concentration at Study Day 42 is anticipated to be near steady state.

The SMC will independently review cumulative safety surveillance data throughout the study and make recommendations regarding the study progression. The SMC can stop study entry and dosing as it deems necessary.

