All patients should receive their usual medications in unchanged doses during the entire treatment period. If a patient clinically deteriorates in the judgment of the investigator the investigator is permitted to add new or increase existing immunosuppressive medications, as long as no prohibited medications are added. Concurrent immunosuppressive therapy may be tapered and discontinued, according to the investigator's judgment, during the follow-up period.

Patients are considered evaluable if they receive the first 4 doses of study drug (MEDI-545 or placebo) and complete the required evaluations, or if they discontinue study drug administration at any time for safety reasons. Nonevaluable patients may be replaced to maintain a size of at least 8 patients per dose cohort. Data from all patients will be included in safety analyses. A dose cohort may be expanded by up to 4 additional patients (for a maximum of 20 additional patients in total) if eligible patients are in screening at the time 8 patients have been randomized into the dose cohort.

Study drug administration will start on Study Day 0 and continue through Study Day 182. At the end of the treatment period, patients will be followed for 24 weeks, through Study Day 350. Safety parameters including assessments of adverse events (AEs) and serious adverse events (SAEs) will be assessed at every study visit from the signing of informed consent through Study Day 350. The occurrence of treatment-emergent AEs and SAEs will be summarized from the first administration of study drug through Study Day 350. Disease activity will be assessed throughout the treatment period and during follow-up.

Decisions regarding dose escalation will be made by the Medical Monitor based on the review of all cumulative, blinded safety information which includes the safety data through Study Day 42 from the first 8 evaluable patients in each of the preceding lower dose cohorts.

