Patients are considered evaluable if they receive the first 4 doses of study drug (MEDI-545 or placebo) and complete the required evaluations, or if they discontinue study drug administration at any time for safety reasons. Nonevaluable patients may be replaced to maintain a size of at least 8 patients per dose cohort. Data from all patients will be included in safety analyses. A dose cohort may be expanded by up to 4 additional patients (for a maximum of 20 additional patients in total) if eligible patients are in screening at the time 8 patients have been randomized into the dose cohort.

Study drug administration will start on Study Day 0 and continue through Study Day 182. At the end of the treatment period, patients will be followed for 24 weeks, through Study Day 350. Safety parameters including assessments of AEs and SAEs will be assessed at every study visit from the signing of the informed consent through Study Day 350. Disease activity will be assessed throughout the treatment period and during follow-up. Patient evaluations are described in Table 4 and Table 5.

Decisions regarding dose escalation will be made by the Medical Monitor based on the review of all cumulative, blinded safety information which includes the safety data through Study Day 42 from the first 8 evaluable patients in each of the preceding lower dose cohorts (Section 4.9).

The study schema is described in Figure 1.

[figure not shown]

Figure 1 Study schematic

Patients who participate in this study may have the option of entering a long-term safety study (MI-CP212). This includes both MEDI-545 and placebo patients, but excludes patients who discontinued from previous MEDI-545 clinical studies for safety reasons. Patients must complete the treatment period and follow up through Day 266 of this study to participate in MI-CP212. Patients must also qualify for the long-term safety study (following written informed consent), as per the MI-CP212 protocol inclusion and exclusion criteria. If patients qualify, they will receive open-label MEDI-545. Patients may be treated for approximately 3 years and may be followed for an additional 3 months following the last dose of IV MEDI-545.

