3.2 Patient Randomization Procedures and Treatment Allocation

Patients will be screened by investigators or qualified designees to assess eligibility for randomization into the study. Screening of patients will be managed so that about 40% to 60% of randomized patients will have DM and the remainder PM. A master log will be maintained of all consented patients and will document all screening failures, including the reason for screening failure.

Treatment assignments will be determined using a central randomization procedure through an interactive voice response system (IVRS). Patients with a median fold overexpression of the top 25 type I IFN inducible genes of 4-fold or greater in whole blood or muscle will be randomized to Dose Cohorts 1, 2, 3A, or 4, and patients with low/undetectable expression of type I IFN-inducible genes will be randomized to Dose Cohort 3B. Central randomization will be applied without regard to site.

The randomization procedure is as follows:

- Investigator or qualified designee confirms the patient meets all eligibility criteria and has signed an informed consent;
- MedImmune calls the IVRS before Study Day 0 to provide the results of type I IFN gene signature in the patient;
- The IVRS notifies the investigator or qualified designee that the patient may be randomized into the study;
- Investigator or qualified designee calls the IVRS on Study Day 0 and provides at a minimum the initials, date of birth, body weight of the patient, and the clinical diagnosis;
- The IVRS randomly assigns a treatment (MEDI-545 or placebo) to the patient along with a PID and blinded study drug kit number to be used for that patient; and
- A confirmatory fax or e-mail with this information is sent to the investigator or qualified designee.

When a patient is assigned a PID by the IVRS the patient is considered randomized into the study.

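### The dose-escalation gate is defined on two different sets of 8 patients: evaluable in the Abstract and Section 2.4.1, randomized in Section 4.9

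*Protocol*

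**What the plan says.** Section 2.4.1 has the Medical Monitor decide on escalation from the blinded cumulative record, "which includes the safety data through Study Day 42 from the first 8 evaluable patients in each of the preceding lower dose cohorts". It points the reader to Section 4.9 for the detail. The Abstract uses the same population: "from the first 8 evaluable patients in each of the preceding lower dose cohorts".

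The rules themselves are in Section 4.9. There the review, also through Day 42, takes its data "from the first randomized 8 patients in each of the preceding lower dose cohorts and all cumulative safety data available in all cohorts".

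The protocol defines the two populations differently:

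- **Evaluable** (Section 2.4.1): "Patients are considered evaluable if they receive the first 4 doses of study drug (MEDI-545 or placebo) and complete the required evaluations". A patient who stops study drug at any time for safety reasons also counts.
- **Randomized** (Section 3.2): "When a patient is assigned a PID by the IVRS the patient is considered randomized into the study". No dose is required.

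Section 3.2 itself provides for a patient among the first 8 who is randomized but untreated, or who is not evaluable. That patient's treatment assignment passes to the ninth patient enrolled. Section 2.4.1 makes replacement optional, and Section 4.9 does not mention it.

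**The concern.** In a trial whose primary objective is safety, this gate is the only prospective rule that fixes how many patients must be observed before a higher dose opens. With two definitions, the same cohort can pass under one and fail under the other. The patients who make the difference are those who received fewer than four doses and stopped for a reason other than safety: Section 4.9 counts them and Section 2.4.1 does not. An auditor could not tell from the text whether a given escalation complied.

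The randomized wording also weakens the reason Section 4.9 gives for choosing Day 42, namely that serum concentration is near steady state by then. That is true only of patients who are still being dosed.

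**Working it through.** **1. Are the two sets really different?** By Table 4, the first four doses fall on Days 0, 14, 28 and 42. Take a patient who receives one dose and stops for a non-safety reason.

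- Section 2.4.1: not evaluable, so not one of the 8.
- Section 4.9: has a patient number, so is one of the first 8 randomized.
- Section 3.5: treated patients are followed whatever number of doses they received, unless consent for follow-up is withdrawn. This patient can therefore supply Day 42 data.
- Section 3.2: any replacement is the ninth patient enrolled, and so, read literally, falls outside the first 8 randomized.

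The same cohort meets the gate in Section 4.9 and fails the one in Section 2.4.1.

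**2. The Day 42 rationale.** Section 4.9 gives a half-life of 15 to 18 days, and dosing is every 14 days. Under simple accumulation, the fraction of steady state after k intervals is 1 − 2^(−14k/t½).

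| Intervals | t½ = 15 days | t½ = 18 days |
|---|---|---|
| 1 (one dose given) | 47.6% | 41.7% |
| 3 (Day 42, before the fourth dose) | 85.6% | 80.2% |

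A patient who stops after one dose reaches about 42% to 48% of steady state and then declines, against 80% to 86% for one dosed on schedule.

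**3. The protocol's own precision figures.** Section 5.2 tabulates one cohort of 6 active patients. Table 7, at a true rate of 6.5%: 1 − (1 − 0.065)^6 = 33.2%, as printed. Table 8, zero events in 6: the exact upper 95% limit is 1 − 0.025^(1/6) = 45.9%, as printed. The remaining rows of both tables also reproduce.

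**4. The same figures with fewer informative active patients.** Each nonevaluable active patient is counted as giving no information, which is the upper end of the loss.

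| Active patients counted | Chance of at least one event at 6.5% | Upper 95% limit, zero events |
|---|---|---|
| 6 | 33.2% | 45.9% |
| 5 | 28.5% | 52.2% |
| 4 | 23.6% | 60.2% |

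**5. How often could this happen?** The protocol gives no rate of non-safety dropout before the fourth dose. Assuming 5% to 20% per patient, independently, the chance that at least one of 6 active patients is nonevaluable runs from 1 − 0.95^6 = 26.5% to 1 − 0.80^6 = 73.8%. The expected number of active evaluable patients runs from 6 × 0.95 = 5.7 down to 6 × 0.80 = 4.8. Section 3.3 keeps the Medical Monitor blinded, so the monitor could not tell whether a nonevaluable patient was one of the 6 on active drug or one of the 2 on placebo.

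**The case against.** The best defence is that the mismatch is a matter of wording within a well-supervised escalation. Section 4.9 also requires review of all cumulative safety data. The Safety Monitoring Committee reviews the Medical Monitor's escalation decisions (Section 4.6) and can stop entry and dosing. Section 4.8 halts the affected and higher cohorts after listed events. Early leavers are still followed, and their data enter the safety analyses, so they are not worthless. All of this stands and lowers the stakes. None of it fixes the minimum number of patients exposed through four doses before the next dose opens.

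Three stronger readings are tempting, and the document does not support them.

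- **That the 8 could freely include patients never dosed.** Section 4.9 asks for data through Day 42 from those 8, and an undosed patient has no on-drug data to give. The wording does not exclude such a patient, since replacement is optional and not tied to the gate, but this is not the natural reading.
- **That the protocol contradicts itself on whether Cohort 3B must be reviewed before Cohort 4.** The Abstract, Section 2.4.1 and Section 4.9 use the same general phrase about preceding lower cohorts. Section 4.9 then names 3A as the gate for Cohort 4 and adds "Dose Cohorts 3B and 4 will enter patients in parallel". A cohort running in parallel need not be a preceding one. The general phrase is loose, because 3B is also a 3.0 mg/kg cohort, but the design decision is explicit.
- **That the loss of information is known to be large.** No dropout rate is given, so the figures above are illustrations.

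It may also be said that the matter is largely past. Section 1.5 reports 51 patients dosed. The four cohorts other than Cohort 4 hold at most 4 × 12 = 48 when fully expanded, leaving replacements aside, so Cohort 4 was probably open by then. That moves the weight toward documenting which population was used. It does not show that any escalation was wrong.

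**Conclusion.** The contradiction between evaluable and randomized is real, lies in current text and concerns a safety decision rule, so it should be corrected. Read literally, Section 4.9 can be satisfied with less exposure than the Abstract and Section 2.4.1 promise.

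The effect is modest if one active patient is affected: detection at the 6.5% rate drops by 33.2 − 28.5 = 4.7 percentage points, and the zero-event limit rises by 52.2 − 45.9 = 6.3 points. With two affected, the changes are 33.2 − 23.6 = 9.6 and 60.2 − 45.9 = 14.3 points. These sizes rest on two assumptions: that such patients occur, which the document neither states nor excludes, and that they contribute nothing, which overstates the loss.

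Two smaller points are editorial. Section 4.9 leaves it to the reader whether 3B counts under the general phrase. It also describes the first cohort as a single-dose cohort ("Dose Cohort 1 (single-dose, 0.3 mg/kg or placebo) will be started first"), whereas Table 1 gives that cohort 7 plus 7 doses. The slip does not change the gate.

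**What to change.** 1. Use one definition of the 8 gate patients in the Abstract, Section 2.4.1 and Section 4.9, and state whether a replacement counts toward the 8.
2. For any escalation already made, record which population was used and how many patients had received four doses by Day 42.
3. As clarifications in Section 4.9, say whether 3B counts as a preceding lower cohort, and delete the single-dose description of Cohort 1.

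Which gate is clinically right is for the sponsor's safety physicians; none is proposed here. The cost is a wording amendment and a note to file. Depending on the rule chosen, a remaining escalation might have to wait for a replacement patient to reach Day 42.

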4.10 Monitoring of Dose Administration

As with any antibody, infusion reactions and IgE-mediated allergic reactions to dose administration are possible. Therefore, appropriate drugs and medical equipment to treat infusion reactions and acute allergic reactions must be immediately available, and study personnel must be trained to recognize and treat anaphylaxis.

5 STATISTICAL CONSIDERATIONS

5.1 General Considerations

All data will be provided in data listings sorted by treatment group and patient number. All tabular summaries will be presented by treatment group. Categorical data will be summarized by the number and percentage of patients in each category. Continuous variables will be summarized by descriptive statistics including mean, standard deviation, median, minimum, and maximum. No formal statistical tests are planned. Missing data will be treated as missing. No data will be imputed unless otherwise specified. Study Baseline values will be defined as the last valid assessment prior to the first administration of study drug. All data will be collected from screening through Study Day 350.

5.2 Sample Size

For the study, 40 patients (5 dose cohorts of 8 patients each) will be randomized into the study. Within each dose cohort, 6 patients will initially receive MEDI-545 and continue receiving MEDI-545 for 14 doses in total; 2 patients will initially receive 7 doses of placebo followed by 7 doses of MEDI-545. In addition, a dose cohort may be expanded by up to 4 additional patients if eligible patients are already in screening at the time 8 patients have been randomized into the dose cohort. Sample size was not based on a formal statistical calculation, but based on clinical considerations as well as the primary objective of safety assessment.

Table 7 and Table 8 present the probability of observing at least one subject with an infrequently occurring AE when assuming a range of potential observed AE rates and exact binomial 95% confidence intervals to assess the precision of estimates of the AE rate for the MEDI-545 single cohort n=6 and for the combined cohorts (n= 12, 18, 24, and 30 respectively) before Study Day 98.

Table 7 Expected Numbers of Subjects with Adverse Events and Probabilities of Observing at Least 1 or 2 Subjects with Adverse Events Given The True Event Rates

N	True Event Rate (%)	Number of Subjects with Events Expected	Probability of Observing at Least One Subject with an Event (%)	Probability of Observing at Least Two Subjects with Events (%)
6	0.8	0	4.7	0.1
6	6.5	0	33.2	5.3
12	0.5	0	5.8	0.2
12	3.0	0	30.6	4.9
18	0.3	0	5.3	0.1
18	2.0	0	30.5	5.0
24	0.2	0	4.7	0.1
24	1.5	0	30.4	5.0
30	0.2	0	5.8	0.2
30	1.5	0	36.5	7.4

Table 8 Estimated Event Rates and 95% Exact Binomial Confidence Intervals Given The Numbers of Subjects with Adverse Events Observed

N	Number of Subjects with Events Observed	Estimated Event Rate (%)	95% Confidence Interval
6	0	0.0	(0.0%, 45.9%)
6	1	16.7	(0.4%, 64.1%)
6	2	33.3	(4.3%, 77.7%)
12	0	0.0	(0.0%, 26.5%)
12	1	8.3	(0.2%, 38.5%)
12	2	16.7	(2.1%, 48.4%)
18	0	0.0	(0.0%, 18.5%)
18	1	5.6	(0.1%, 27.3%)
18	2	11.1	(1.4%, 34.7%)
24	0	0.0	(0.0%, 14.2%)
24	1	4.2	(0.1%, 21.1%)
24	2	8.3	(1.0%, 27.0%)
30	0	0.0	(0.0%, 11.6%)
30	1	3.3	(0.1%, 17.2%)
30	2	6.7	(0.8%, 22.1%)

5.3 Patient Populations

The patient population analyzed will include all patients who receive at least one dose of study drug.

Safety results will be analyzed in all patients who receive any study drug. Evaluability for analyses of MEDI-545 serum concentrations and PK parameters will be determined based upon the frequency and timing of the serum samples obtained. IM analysis will be performed in all patients who have received at least one dose of MEDI-545. Efficacy results will be analyzed in all randomized patients who receive any study drug.

5.4 Study Endpoints

5.4.1 Primary Endpoints

The primary endpoints of the study are the safety and tolerability of MEDI-545, which will be assessed primarily by summarizing treatment-emergent AEs/SAEs and by assessing changes in viral cultures and titers, including oropharyngeal swabs for herpes simplex virus HSV-1 and HSV-2; vaginal swabs for HSV-1, HSV-2, and HPV; and peripheral blood test (using polymerase chain reaction tests) for EBV and cytomegalovirus. The occurrence of treatment-emergent AEs and SAEs will be summarized from the first administration of study drug through Study Day 350. AEs and SAEs occurring after administration of study drug will be coded using the current version of MedDRA and will be summarized by system organ class and preferred terms, by severity, and by relationship to study drug. AEs and SAEs will be summarized for placebo, each of the MEDI-545 dose cohorts, and for all MEDI-545 doses combined. Since patients initially randomized to placebo will receive placebo for the first 7 doses and MEDI-545 for the next 7 doses, AEs and SAEs will also be reported with respect to different treatment periods. The rate of virus detection by surveillance testing will be summarized descriptively.

No formal statistical testing will be performed to compare treatment groups. Other variables used for the safety assessments include serum chemistry, CBC with differential and platelets, and urinalysis. These variables as well as their changes from baseline will be summarized descriptively.

5.4.2 Secondary Endpoints

The secondary endpoints of the study are the PK and IM of multiple IV doses of MEDI-545 and evaluations of disease activity. PK parameters such as peak concentration (C_{\max}), time to peak concentration (T_{\max}), area under the concentration curve within a dosing interval (AUC_{τ}) after the first dose will be estimated. PK parameters at steady state such as peak concentration ($C_{ss, \max}$) and trough concentration ($C_{ss, \min}$) at steady state, time to peak concentration at steady state ($T_{ss, \max}$), area under the concentration curve within a dosing interval at steady state ($AUC_{ss, \tau}$), total body clearance at steady state (CL_{ss}), steady state volume of distribution (Vd_{ss}), terminal phase volume of distribution (Vd_z) and terminal phase half-life ($T_{1/2}$) will also be estimated. All PK parameters will be estimated by non-compartmental analysis. The highest observed concentration will be recorded as C_{\max} and the time to C_{\max} will be recorded as T_{\max} . Terminal phase elimination rate constant (λ_z) will be estimated by regression of the linear portion of the post-absorption serum concentration-time profile after the last dose and $T_{1/2}$ will be estimated as the ratio of natural log and λ_z . The area under the curve within a dosing interval will be estimated using the linear trapezoidal rule. Total body clearance at steady state (CL_{ss}) will be estimated as the ratio of dose and $AUC_{ss, \tau}$. Steady state volume of distribution will be estimated as the product of mean residence time (MRT) and CL_{ss} . Terminal phase volume of distribution will be estimated as the ratio of CL_{ss} and λ_z . Accumulation to steady state will be assessed as the ratio of $C_{ss, \max} : C_{\max}$ and $AUC_{ss, \tau} : AUC_{\tau}$.

MEDI-545 IM will be analyzed by summarizing the number and percentage of PM/DM patients who develop detectable anti-MEDI-545 antibodies by treatment and dose cohort.

